6.1.2. Safety

An SCCS design (Figure 1) will be used. For patients receiving only 1 dose of RZV, the date of vaccination with the first dose of RZV will be defined as Day 0, the risk period will be defined as +1 to +30 days, and comparison periods will be defined as -90 to -61 days and +31 to +60 days (Figure 1, Individuals received only one dose). The washout period will be defined as -60 to -1 days. The 30-day risk period was determined based on prior literature, vaccine mode of action, and consultation with external physician experts (rheumatologists and gastroenterologists) [Basra, 2012; Didierlaurent, 2017].

For individuals who receive a second dose of RZV within 300 days of the first RZV dose, there are several scenarios for additional risk and comparison periods. If the second dose is received between +28 to +90 days after the first dose, the risk period after the first dose will be immediately followed by a washout period up to receipt of the second dose (Figure 1, Scenario 1). If the second dose is received between +91 to +150 days after the first dose, the risk and comparison periods following the first dose will be followed by a 60-day washout period immediately before the receipt of the second dose (Figure 1, Scenario 2). If the second dose is received between +151 days to +300 days after the first dose (expected to be less common), there will be a comparison period -90 to -61 days prior to the second dose and a washout period -60 to -1 days prior to the second dose (Figure 1, Scenario 3). In Scenario 1, the risk window after the first dose could be between 28 and 30 days and the subsequent washout window could be between 0 and 60 days. In Scenario 2, the comparison window between 2 doses could be between 1 and 60 days. The maximum follow-up period will be 360 days after the first dose. Scenarios 2-4 in Figure 1 represent the maximum time period between the first and second dose

Figure 1 SCCS Design Overview for Safety Analysis

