6.2.2. Safety

The outcome for primary safety objectives 1-2, secondary safety objective 1, and exploratory safety objectives 1-2 is flare, defined as new-onset flare or new-onset of disease worsening of RA (primary safety objective 1, exploratory safety objective 1) or IBD (UC or CD) (primary safety objective 2, secondary safety objective 1, exploratory safety objective 2). Flare will be identified through EHR review by trained research associates and RA or IBD specialists. Events are counted in the period in which earliest symptom onset occurs. Clinically relevant flare is described in [Appendix 2](#).

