7.2. Inclusion and exclusion criteria (Eligibility criteria)

7.2.1. Inclusion criteria

Individuals with at least 2 health care encounters with assigned ICD-10 codes for RA or IBD (UC or CD) in the year prior to and including the index date will be identified from the EHR, as specified below. This algorithm was selected based on the literature [MacLean, 2000; Weng, 2007] and KPSC chart review indicated a high positive predictive value of this approach.

Rheumatoid arthritis ICD-10 Codes

- M05.* - Rheumatoid arthritis with rheumatoid factor
- M06.* - Other rheumatoid arthritis

Crohn's disease ICD-10 Codes

- K50.* - Crohn's disease

Ulcerative colitis ICD-10 Codes

- K51.* - Ulcerative colitis

The population for primary VE objective 1, secondary VE objectives 2 and 4-6, and exploratory VE objectives 1 and 3 will be drawn from individuals with RA, and the population for primary VE objective 2, secondary VE objectives 1, 3-5, and 7, and exploratory VE objectives 2 and 4 will be drawn from individuals with IBD (UC or CD).

Similarly, the population for primary safety objective 1 and exploratory safety objective 1 will be drawn from individuals with RA, and the population for primary safety objective 2, secondary safety objective 1, and exploratory safety objective 2 will be drawn from individuals with IBD (UC or CD).

While co-occurrence of both conditions in the same individual is expected to be rare, individuals with both RA and IBD will be included in analyses for both conditions.

Individuals will be included in the study if they meet the following criteria:

VE

- Aged ≥ 18 years at index date
- At least 1-year of continuous KPSC membership prior to the index date and until 31 days after index date (allowing for a 31-day gap in membership)

Safety

- Received ≥ 1 dose of RZV
- Aged ≥ 18 years at date of first RZV dose
- At least 1-year continuous KPSC membership prior to date of first RZV dose (allowing for a 31-day gap in membership)

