13.2. Appendix 2: Definition of clinically relevant flare

Definition of “clinically relevant” flare

For this study, flare is defined as clinically relevant new-onset flare or new-onset disease worsening of RA (primary safety objective 1, exploratory safety objective 1) or IBD (UC or CD) (primary safety objective 2, secondary safety objective 1, exploratory safety objective 2). This definition was selected in consultation with rheumatologist and gastroenterologist experts, recognizing that new-onset disease worsening can be difficult to differentiate from flare. Trained research associates and RA or IBD specialists will review all potential flare events, according to the following case definition:

1. Contact with health care provider via documented phone call, email, telehealth visit, or in-person office, Emergency Department, or inpatient visit, AND
2. New or worsening signs and/or symptoms suggestive of a flare (at least one of the signs or symptoms below):
 - a. RA – joint swelling, joint pain/tenderness, joint stiffness.
 - b. IBD – abdominal pain/tenderness, diarrhea (increased stool frequency and/or soft or liquid stool), urgency, rectal bleeding, blood in stool, nausea/vomiting, unintentional weight loss.
 - c. Provider mention of flare, worsening of disease, recurrence, or relapse

AND

1. Change in medication for flare*:

Proposed medication regimen change/escalation algorithm for flare

- a. Intra-articular corticosteroid joint(s) injection (for RA), or
- b. Initiation of systemic corticosteroid (e.g., prednisone), or
- c. Increase in dose of baseline systemic corticosteroid (e.g., prednisone 5 mg daily to prednisone 40 mg daily with taper), or
- d. Switch in methotrexate (MTX) from oral route to subcutaneous (for RA), or
- e. Increase in dose and/or frequency of administration of any medication in current baseline regimen, or
- f. Addition of another medication to current medication regimen (e.g., MTX to current regimen of hydroxychloroquine [(Plaquenil)], biologic to current regimen of MTX), or
- g. Switch of a current medication to another medication, in the same or different category (e.g., MTX + tumor necrosis factor [TNF]-alpha inhibitor to MTX + tofacitinib; MTX + TNF-alpha inhibitor to MTX + a different TNF-alpha inhibitor)

*Exclude medication changes for any reasons other than for flare, such as acute kidney injury or other adverse effects from prior medication.

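### The flare analysis counts days -90 to -61 as comparison time without requiring RA or IBD to be diagnosed by then, which may bias the relative risk, most likely upward and modestly

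*Protocol*

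**What the plan says.** - **Windows (6.1.2).** For one-dose patients, with day 0 the first dose: "the risk period will be defined as +1 to +30 days"; "The washout period will be defined as -60 to -1 days"; and "comparison periods will be defined as -90 to -61 days and +31 to +60 days". No condition refers to the date of diagnosis. For two-dose patients the section describes additional windows. I read this as leaving the window before dose 1 in place (Figure 1 is not shown).
- **Disease criterion (7.2.1).** Two encounters coded RA or IBD are needed, "in the year prior to and including the index date will be identified from the EHR". Both may fall in the last 60 days. The glossary defines an index date only for the effectiveness objectives; for safety I read it as day 0.
- **Safety criterion (7.2.1).** "At least 1-year continuous KPSC membership prior to date of first RZV dose". This is enrolment in the health plan, not duration of disease.
- **Outcome (6.2.2 and Appendix 2).** A flare needs provider contact, new or worsening symptoms, and a medication change made for flare. The listed changes include starting a systemic corticosteroid and "Addition of another medication to current medication regimen". No prior diagnosis is stated as a condition. "Events are counted in the period in which earliest symptom onset occurs".
- **Chart review (Appendix 2).** Records are read for the windows and the 30 days after each. For the early window this ends at about day -31.

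**The concern.** A self-controlled case series assumes that each person could have the event throughout the observed time. A patient whose first two RA or IBD codes fall in days -60 to 0 is credited with 30 comparison days from before the disease was recognised. If those days cannot hold a flare, they add to the comparison denominator and nothing to its numerator, and the RR rises with no vaccine effect.

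Sections 5.2.1 and 6.3.2 rely on the design to control fixed characteristics, age and season. Time since diagnosis is none of these. The RR is the primary safety estimate, and the EnCePP checklist (item 10.8) says that no sensitivity analyses are planned, so nothing planned would reveal the problem.

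**Working it through.** **1. The plan's own figures.** Table 7 uses the signed root likelihood ratio method with k = 2. With r = 1/3 and D = RR·r + 1 - r:

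- A = 2[(RR·r/D)·ln RR - ln D]
- B = (ln RR)²/A × RR·r(1 - r)/D²
- n = (1.960 + 0.8416·√B)²/A

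At RR = 1.5: D = 1.1667, A = 0.03924, B = 1.026, n = 201.6. The table has 87 + 115 = 202. For RR 1.2, 2 and 3 the formula gives 1030, 68 and 27, against 1029, 68 and 26. Expected comparison flares also reproduce: RA 3071 × 0.025 × 2 = 153.6 (stated 154); IBD 2308 × 0.03 × 2 = 138.5 (stated 138). Both counts treat the two 30-day windows as at risk for everyone.

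**2. Bias formula, one-dose layout.** Let p be the share first diagnosed after day -61. Let q be their recorded event rate in the early window relative to established patients. Rates are equal elsewhere and there is no vaccine effect. Per 30-day window:

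- risk events: 1
- comparison events: 2(1 - p) + p(1 + q) = 2 + p(q - 1)
- estimated RR = 2/[2 + p(q - 1)]

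| p | q = 0 (no early-window event) | q = 2 (first presentations counted) |
|---|---|---|
| 5% | 1.026 | 0.976 |
| 10% | 1.053 | 0.952 |
| 20% | 1.111 | 0.909 |

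The direction turns at q = 1. At the RA planning rate, that is first presentations counted as early-window flares in 2.5% of the recently diagnosed.

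**3. Two-dose layouts.** With q = 0 and C comparison days in total, RR = 1/(1 - 30p/C). I assume 30 comparison days after dose 2.

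- Scenario 1: C = 60, same result as one dose.
- Scenario 2: C from 61 to 120.
- Scenario 3: C = 120, giving 1/(1 - p/4), which is 1.026 at p = 10% and 1.053 at 20%.

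Table 5 implies that about 60% of recipients have two doses (1843/3071).

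**4. False finding of increased risk, q = 0, one-dose layout.** Normal approximation, nominal upper tail 2.5%. RA at p = 10%:

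- events: 3071 × 0.025 × 2.9 = 222.6
- share in risk window: 1.0526/3.0526 = 0.3448
- critical share: 0.3333 + 1.96 × 0.0316 = 0.3953
- upper tail: (0.3953 - 0.3448)/0.0319 = 1.58, or 5.7%

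| p | RA | IBD |
|---|---|---|
| 5% | 3.8% | 3.7% |
| 10% | 5.7% | 5.5% |
| 20% | 11.5% | 10.8% |

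**5. Does restricting the time remove the bias?** Drop the early window for the recently diagnosed, so k = 1 for them. The conditional score at RR = 1 is 1 - 2p × (1/2) - 3(1 - p) × (1/3) = 0, so the estimate is centred on 1 for every p. A single simulated run at p = 5%, 10% and 20% gave 0.99 to 1.02.

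**The case against.** A reader might infer that no flare could ever be recorded in the early window for these patients, so that the RR is certainly inflated. The documents do not support that. Appendix 2 sets no prior-diagnosis condition, events are dated by symptom onset, and charts are read to about day -31. Symptoms starting on day -75, with diagnosis and a steroid start on day -45, could be recorded as an early-window event. This stands: near-impossibility applies only to patients first seen after about day -31, and for the others the error can run the other way.

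A reader might also infer that building up treatment after diagnosis generates apparent flares in days +1 to +30. Appendix 2 limits this. A medication change alone does not qualify, changes made for other reasons are excluded, symptoms must be new or worsening, and reviewers are masked to the precise window. Nothing in the protocol supports a flare rate two or three times higher in the newly diagnosed, so the figures above do not use one.

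The share p may be small. Section 3.1 describes RZV as routine from age 50, and Table 5 places 1099 of 1843 RA and 760 of 1385 IBD two-dose recipients in 2018 to 2021, before the assumed start of use in younger immunocompromised adults. That limits the size but does not close the gap.

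Finally, the start of each person's observation time could be set in the SAP, which is not shown. However, the windows and eligibility that create the problem are fixed in the protocol.

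**Conclusion.** The point holds in limited form. The protocol admits patients first diagnosed after day -61 and counts pre-diagnosis days as comparison time for them.

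The net bias is most likely upward, on the natural reading that a first presentation is not a flare or worsening of RA or IBD. The turning point in q is low, so the direction stays open until the protocol says how first presentations are classified.

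The size is modest: an excess in RR of about 3% to 11% for p between 5% and 20% in the one-dose layout, and about half that with 120 comparison days. This assumes no early-window events in the recently diagnosed and equal flare rates otherwise; p is an assumption throughout. The design is sized for RR = 1.5, and power is not the issue: with q = 0 and p = 20%, expected comparison flares are 153.6 × 0.9 = 138 in RA and 138.5 × 0.9 = 125 in IBD, both above the 115 required. What is at stake is a small spurious excess in a primary safety estimate.

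**What to change.** In 7.2.1, require for the safety population a first recorded RA or IBD code before day -90. This removes the bias in either direction.

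Alternatively, in 6.1.2, start each person's observation at the first recorded RA or IBD code, drop earlier comparison days, and state in Appendix 2 that the first presentation of disease is not counted as a flare. The last clause is needed because events are dated by symptom onset, which can precede the first code.

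Either option needs one date from diagnosis data already extracted. The cost is lost subjects, or lost comparison days, among recently diagnosed patients only. Under exclusion, expected comparison flares at p = 10% are 153.6 × 0.9 = 138 (RA) and 138.5 × 0.9 = 125 (IBD). At p = 20% they are 123 and 111, the latter just under 115. If p proves that large, the second option keeps more of the data.

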6.2. Outcomes (VE and Safety)

6.2.1. VE

HZ

The primary outcome is HZ, identified by ICD-10 code B02.xx in any health care setting (outpatient [to include virtual visits], inpatient, Emergency Department) AND a prescription for a non-topical antiviral (acyclovir, valacyclovir, famciclovir) in the 7 days before or after the HZ diagnosis code date, without a non-topical antiviral (acyclovir, valacyclovir, famciclovir) prescribed in the 183 days to 8 days prior to the HZ diagnosis code date [Langan, 2013; Tseng, 2020]. The first eligible HZ diagnosis after the index date will be considered an incident HZ event.

PHN

PHN will be defined as HZ-related pain persisting ≥ 3 months after HZ diagnosis. HZ-related pain will be defined as pain consistent with the HZ episode which is not explained by other obvious causes. Targeted chart review will be used to identify PHN from encounters in the ≥ 3 to 6-month period after HZ diagnosis. Given the potential for poor positive predictive value and negative predictive value for PHN using only automated data (based on prior work by the KPSC research team), all HZ cases with encounters during ≥ 3 to 6-month period after HZ diagnosis will be chart reviewed for the occurrence of PHN.

Disseminated HZ

Disseminated HZ will be defined as an ICD-10 code for disseminated zoster (B02.7) on or within the 30 days following the incident HZ event date.

HZ-related meningoencephalitis

HZ-related meningoencephalitis will be defined based on ICD-10 codes and laboratory tests among individuals with HZ who are hospitalized during or within the 6 months after the incident HZ event date, based on any of the following criteria: (1) ICD-10 codes for zoster encephalitis (B02.0) or zoster meningitis (B02.1) in the hospital setting, (2) an HZ diagnosis with a cerebrospinal fluid (CSF) PCR or rapid culture test that is positive for VZV, or (3) a herpes viral infection diagnosis (B00.xx) in the hospital setting with a CSF test that is positive for VZV.

Hospitalized HZ

Hospitalized HZ will be identified among incident HZ events with ICD-10 codes for HZ from inpatient encounters or emergency department-to-inpatient transfers.

6.2.2. Safety

The outcome for primary safety objectives 1-2, secondary safety objective 1, and exploratory safety objectives 1-2 is flare, defined as new-onset flare or new-onset of disease worsening of RA (primary safety objective 1, exploratory safety objective 1) or IBD (UC or CD) (primary safety objective 2, secondary safety objective 1, exploratory safety objective 2). Flare will be identified through EHR review by trained research associates and RA or IBD specialists. Events are counted in the period in which earliest symptom onset occurs. Clinically relevant flare is described in [Appendix 2](#).

6.3. Other variable definitions (VE and Safety)

6.3.1. VE

Other variables will be identified from the EHR and considered in analyses when appropriate as covariates, including:

- Demographic variables: age at index date, sex, race/ethnicity
- Health care utilization (number of outpatient [to include virtual visits]/Emergency Department/inpatient encounters) in the year prior to the index date
- Comorbidities (e.g., kidney disease, cardiovascular disease, pulmonary disease [i.e., chronic obstructive pulmonary disease or chronic bronchitis], liver disease, diabetes mellitus, other autoimmune diseases, cancer, immunocompromising conditions [i.e., human immunodeficiency virus, cancer, transplant, immunosuppressive medications], SARS-CoV-2 infection/COVID-19 diagnosis) in the year prior to the index date
- History of ZVL or varicella vaccination prior to the index date based on dates of vaccinations in the EHR
- History of HZ prior to the index date identified using ICD-10 codes (B02.xx) and ICD-9 codes (053.xx) from hospital, outpatient (to include virtual visits), and Emergency Department settings
- Concomitant vaccinations at time of exposure (e.g., receipt of influenza vaccine, pneumococcal vaccine, Tetanus, diphtheria and pertussis vaccine, COVID-19 vaccine)
- Medication category as detailed in [Appendix 3](#).
- Membership history: length of continuous membership (allowing 31 days gap) prior to the index date.

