3.2. Description of the database (Electronic health records)

Kaiser Permanente Health Connect is the largest and most advanced civilian EHR system available in the U.S. In addition to supporting patient care, this robust system facilitates research, providing access to the EHR for the KPSC vaccine research team. Up-to-date details of patient care are available and accessible to researchers. Data regarding demographics, services, and diagnoses are tracked from the outpatient, Emergency Department, and hospital settings.

Pharmacy and vaccination utilization are linked through patients' unique medical record numbers. As KPSC is a pre-paid health care system, recommended vaccines such as RZV are provided to KPSC members at no charge and can be obtained at no-cost nurse visits or on a walk-in basis without appointment, which is an incentive for members to receive immunizations within the system. Vaccinations received outside of the health plan with appropriate documentation are also recorded in KPSC databases.

KPSC members have very strong motivation to use services internally. For outside providers to be reimbursed by the health plan for covered emergent or contract care, claims must be submitted with documentation of the episode of care, which is integrated into KPSC databases. Thus, the capture of care is considered to be very comprehensive. Care received at KPSC is updated and available to researchers in near real time. Claims data are over 90% complete after 3 months.

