5.2.2. Limitations

First, confounding by indication is a potential limitation. For the VE objectives, this will be addressed by matching on condition (RA, UC, CD), age, sex, race/ethnicity (if sample size allows), and medication category, which may impact the development of the outcome and likelihood of RZV vaccination. For the safety objectives, the SCCS design mitigates bias through implicit control for time-fixed confounders. While the short risk window minimizes changes in confounders during follow-up, potential confounders will be assessed and adjusted for in final analysis.

Second, a potential limitation is misclassification of exposures and outcomes. However, receipt of RZV should be accurately captured in the EHR system, including dates of administration such that receipt of dose 1 and dose 2 are correctly ascertained. The effectiveness outcome of incident HZ is expected to be accurately captured using an algorithm based on a combination of an International Classification of Diseases (ICD)-10 code and prescription for an antiviral. This algorithm has been used in previous studies and was found to have high accuracy in identifying incident HZ [Capistran, 2021; Langan, 2013; Tseng, 2020; Zhang, 2012]. Given the complexity and significant potential for misclassification of the safety outcome of disease flare, medical record review using standardized criteria will be performed to ascertain this outcome. Since this study uses EHR data, the effectiveness and safety outcomes being captured are those for which medical attention is sought. Mild outcomes may be missed.

Third, there is a potential concern for missing patient data during the course of follow-up, particularly for the longer follow-up duration required for the primary effectiveness outcome. However, patients within KPSC are incentivized to use care inside the health care system, so it is expected that the majority of care, including rheumatologist and gastroenterologist visits, will occur within network, and that there will be comprehensive longitudinal capture of a patient's baseline disease activity, medication regimens, and flares so long as they remain KPSC members.

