6.1. Exposures (VE and Safety)

RZV vaccine doses will be identified using CVX code 187: Zoster vaccine recombinant.

6.1.1. VE

Although RZV should be administered as 2 doses separated by 2-6 months, ACIP guidance followed at KPSC specifies that a second dose administered <4 weeks after the first dose should be repeated, but a second dose administered ≥ 4 weeks after the first dose does not need to be repeated [Anderson, 2022]. Furthermore, due to variation in real-world practice, the second dose may be given earlier than 2 months after the first dose or later than 6 months after the first dose. Additionally, as of January 21, 2022, ACIP guidelines indicate that the second dose of RZV can be administered 1–2 months after the first dose for individuals who are or will be immunodeficient or immunosuppressed and who would benefit from a shorter vaccination schedule [Anderson, 2022]. Therefore, VE objectives refer to 2 doses of RZV given at least 4 weeks apart through the end of the study accrual, except where indicated otherwise.

The exposure for primary VE objectives 1-2 is 2 doses of RZV with the second dose received 4 weeks to 6 months after the first dose through the end of study accrual. The exposure for secondary VE objectives 1-3 and 5 and exploratory VE objectives 1-4 is 2 doses of RZV, with the second dose received at least 4 weeks after the first dose (“2-dose [≥ 4 weeks]”). The exposure for secondary VE objective 4 is 2 doses of RZV, with the second dose received >6 months after the first dose through the end of study accrual. The index date will be date of receipt of the second RZV dose.

[figure not shown]
The exposure for secondary VE objectives 6-7 is 1 dose of RZV. The index date will be date of receipt of the first RZV dose. The 1-dose VE will be evaluated in individuals who receive 1 dose of RZV and do not receive a second dose within 6 months after the first dose.

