7.4. Matching for VE analyses

For secondary VE objectives 1-3, secondary VE objective 5, and exploratory VE objectives 1-4, individuals meeting inclusion criteria who receive 2 doses of RZV at least 4 weeks apart through the end of the accrual period will be matched with unvaccinated individuals who have not received any doses of RZV as of the index date at a ratio of 1 to up to 3. For secondary VE objective 4, individuals meeting inclusion criteria who receive 2 doses of RZV >6 months apart through the end of the accrual period, and for primary VE objectives 1-2, individuals meeting inclusion criteria who receive 2 doses of RZV 4 weeks to 6 months apart, and their respective matched unvaccinated comparators will be included. No separate matching is needed.

Matching variables will comprise the following:

- Condition (RA, UC, CD)
- Age (by decade) at index date
- Sex
- Race/ethnicity, if sample size allows
- Medication category at index date (detailed in [Appendix 3](#)).

For secondary VE objectives 6-7, individuals who receive 1 dose of RZV but do not receive a second dose 4 weeks to 6 months after the first dose will be matched with unvaccinated individuals who have not received any doses of RZV as of the index date at a ratio of 1 to up to 3. The 1-dose person-time will be censored upon receipt of the second RZV dose received >6 months after the first dose. Matching variables will comprise condition (RA, UC, CD), age (by decade) at index date, sex, race/ethnicity (if sample size allows), and medication category at index date.

The 2-dose (4 weeks to 6 months) RZV cohort and 1-dose RZV cohort will be mutually exclusive. Unvaccinated individuals who are matched to RZV vaccinated individuals can contribute person-time to a vaccinated cohort if they receive RZV; their unvaccinated person-time is censored upon receipt of the first dose of RZV.

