11.2.2. Primary analyses

For primary VE objectives 1-2, the number of incident HZ cases and the number of person-years of follow-up for subjects will be assessed for the 2-dose (4 weeks to 6 months) RZV cohort and the matched unvaccinated cohort.

Unadjusted and adjusted HRs and 95% confidence intervals (CIs) comparing HZ incidence rates in the 2-dose (4 weeks to 6 months) RZV cohort and the matched

unvaccinated cohort will be estimated by Cox stratified proportional hazards regression models without and with adjusting for potential confounders described above. Estimates of VE (%) will be calculated as $(1 - \text{HR}) \times 100$ when the HR is less than or equal to 1, and $([1/\text{HR}] - 1) \times 100$ when the hazard ratio is greater than 1.

The VE of 2 doses of RZV by time since vaccination will also be evaluated.

For the primary safety analyses, characteristics of individuals with RA or IBD who meet inclusion criteria will be described. Incidence rates for RA or IBD (UC or CD) flare for risk periods and comparison periods will be calculated by dividing the number of flares by person-time. Relative risks (95% CI) for flare comparing risk and comparison periods overall and by first dose and second dose will be estimated using conditional Poisson regression.

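### In the 2-dose VE analyses the utilization look-back contains dose 1, so a vaccination-only visit can be counted as baseline care-seeking for vaccinated people only

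*Protocol*

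**What the plan says.** Section 6.3.1 defines the covariate as "Health care utilization (number of outpatient [to include virtual visits]/Emergency Department/inpatient encounters) in the year prior to the index date". It is one of several variables to be "considered in analyses when appropriate as covariates".

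Section 6.1.1 fixes the timing for the 2-dose objectives: "The index date will be date of receipt of the second RZV dose". For primary VE objectives 1-2 the exposure is "2 doses of RZV with the second dose received 4 weeks to 6 months after the first dose".

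Section 7.4 draws the comparators from "unvaccinated individuals who have not received any doses of RZV as of the index date".

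Section 11.2.2 reports Cox hazard ratios "without and with adjusting for potential confounders described above", and utilization is among the variables described.

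Section 3.2 says that RZV "can be obtained at no-cost nurse visits or on a walk-in basis without appointment". The protocol does not say whether such a contact counts as an outpatient encounter. No rule removes it from the count.

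**The concern.** Utilization is on the list to measure how readily a person sought care before exposure. Under this definition the look-back also spans the first part of the vaccine course, and only in one group. A visit made to receive dose 1 is part of the exposure, yet it could be entered as baseline behaviour.

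A covariate that carries a piece of the exposure distorts the adjusted comparison. If each extra visit goes with more recorded HZ, the model expects too many cases among the vaccinated and credits the vaccine with the difference. It would also touch the standardized differences that section 11.2.1 uses to judge balance. The EnCePP checklist (item 10.8) states that no sensitivity analyses are planned, so none would reveal it.

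**Working it through.** The protocol gives no figure for this effect, so there is none to reproduce. The check has four steps.

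**1. Does dose 1 fall in the look-back?**

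- Primary objectives: the gap from dose 1 to the index date is 4 weeks to 6 months, which is less than one year. Always yes.
- Secondary objective 4 (second dose more than 6 months after the first) and the analyses of any gap of at least 4 weeks: yes when the gap is under a year, otherwise no.
- 1-dose objectives: the index date is dose 1, so there is no earlier RZV visit. No.
- Comparators: no RZV dose by the index date. No.

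The dose-2 visit is on the index date itself, so a count prior to that date leaves it out.

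**2. Effect on the adjusted hazard ratio.** Let θ be the true HR, V vaccination (0 or 1), U the true baseline visit count and r the hazard ratio per visit. The hazard is proportional to θ^V × r^U. If every vaccinated person carries one artificial visit, the recorded count is U* = U + V. Substituting U = U* − V gives (θ/r)^V × r^U*. So

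adjusted HR = θ / r, and adjusted VE = 1 − θ/r.

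θ is taken from the planning range in section 11.1.1 (HR 0.1 to 0.4). r is not in the protocol; 0.97 to 1.10 is an assumed range.

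| True VE | r = 0.97 | r = 1.00 | r = 1.01 | r = 1.03 | r = 1.05 | r = 1.10 |
|---|---|---|---|---|---|---|
| 60% | 58.8 | 60.0 | 60.4 | 61.2 | 61.9 | 63.6 |
| 70% | 69.1 | 70.0 | 70.3 | 70.9 | 71.4 | 72.7 |
| 80% | 79.4 | 80.0 | 80.2 | 80.6 | 81.0 | 81.8 |
| 90% | 89.7 | 90.0 | 90.1 | 90.3 | 90.5 | 90.9 |

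For example, at VE 70% and r = 1.05: 1 − 0.30/1.05 = 71.4%.

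If only half of the vaccinated carry the extra visit, the shift in log HR is roughly halved: 1 − 0.30/√1.05 = 1 − 0.30/1.0247 = 70.7%.

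**3. Simulation check.** Cox models were fitted to simulated cohorts (20,000 vaccinated, 60,000 unvaccinated, true VE 70%, 15 cases per 1000 person-years, 3.5 years, mean 10 visits), on the same data with and without the extra visit. Utilization was entered as a count or in four bands. VE moved by +0.2 to +0.3 points at r = 1.01, +0.8 to +0.9 at 1.03, +1.4 to +1.5 at 1.05, and about −0.8 at 0.97. This agrees with the formula.

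**4. Size against sampling error.** RA cohort: 1843 vaccinated (Table 5), 3.5 years, 15/1000, 1:3 matching, VE 70%, before censoring.

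- Vaccinated cases: 1843 × 3.5 × 0.015 × 0.30 ≈ 29.
- Comparator cases: 3 × 1843 × 3.5 × 0.015 ≈ 290.
- SE(log HR) ≈ √(1/29 + 1/290) ≈ 0.195, giving a 95% CI for VE of about 56% to 80%.
- Shift: ln 1.01 = 0.010 and ln 1.05 = 0.049, which is 5% to 25% of one SE.

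For IBD (1385 vaccinated) the same steps give about 22 and 218 cases, SE about 0.225 and a CI of about 53% to 81%. The shift is then a smaller fraction of the SE. Censoring would raise both SEs.

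**The case against.** The strongest reply is that several links are not in the protocol. It does not say that a vaccination-only contact is an encounter, and section 3.2 mentions vaccination utilization apart from the outpatient, emergency and hospital data. A dose given at a visit that would have happened anyway adds nothing, and a dose received outside the plan need not create an encounter. Utilization is a conditional covariate, and its form and place in the model may be settled in the SAP. Unadjusted VE is reported alongside and does not use it.

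These points stand, and they rule out three stronger readings that a reader might infer:

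- That every vaccinated person gains at least one visit. This is an upper bound, not something the protocol implies.
- That the error always favours the vaccine. The sign follows the association between utilization and HZ, which the protocol does not give. Section 5.2.2 makes a positive one plausible, "Since this study uses EHR data, the effectiveness and safety outcomes being captured are those for which medical attention is sought", but a negative one would lower VE.
- That a comparison of 1-dose with 2-dose VE is distorted. No such contrast is planned; each vaccinated cohort is compared with its own matched unvaccinated group.

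What the reply does not remove is the window. It is stated, it spans dose 1 in the primary cohorts, and it can hold an RZV visit in one group only. That is a property of the written definition, not a detail merely left for later.

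**Conclusion.** The point holds as a possible, small, differential artefact in adjusted 2-dose VE. It needs two conditions: vaccination-only visits are recorded as outpatient encounters, and utilization is in the final model. If more visits then go with more recorded HZ, VE is slightly overstated: by about 0.3 to 1.4 points at a true VE of 70%, for an assumed 1.01 to 1.05 per visit and an extra visit in every vaccinated person. That is at most about a quarter of one standard error in the planned RA cohort. It would not change the study's conclusion. The case for acting is that the correction is nearly free and the artefact serves no purpose.

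**What to change.** In section 6.3.1, add that encounters solely for RZV administration are excluded from the utilization count, and apply this in every VE model so that the covariate has one meaning throughout. Keep the one-year look-back before the index date.

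Ending the look-back the day before dose 1 instead is not advisable. In the primary cohorts it could reach 6 + 12 = 18 months before the index date, while section 7.2.1 guarantees only one year of membership before that date. Counts would be incomplete for some people, or eligibility would have to be tightened.

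The cost is one sentence and a small change to covariate extraction, which can use the RZV dose dates already identified by CVX code. Matching, eligibility and sample size do not change.
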